criteria. Subjects who meet the initial screening criteria will be scheduled for a complete screening at the Michigan Clinical Research Unit (MCRU), Frankel Cardiovascular Center (CVC), Domino Farms, or the Central Campus Recreation Building (CCRB). At this time, more specific details about the study will be provided along with answers to any questions. Each study procedure and all possible risks related to these procedures will be explained along with sample exercise programs and explanation of the randomization methods of the study. Verbal and written informed consent will be obtained during this initial visit according to the guidelines of our Institutional Review Board. A study team member will perform a comprehensive medical history. Additionally, participants will complete a venipuncture blood draw and urine collection for laboratory assessment of complete blood count (CBCD), comprehensive metabolic panel (COMP), urinary analysis (UA), urinary microalbumin (UMA), hemoglobin A1C (A1C), thyroid stimulating hormone (TSH), and lipid panel. Females will also be asked to provide urine for a pregnancy test (for premenopausal women). In addition, participants will complete a supervised 12-lead resting electrocardiogram and graded exercise stress test (with VO₂) at the CVC or Domino Farms. EKG test results will be reviewed by a study physician. If any blood work or EKG results are clinically significant, the participant will be notified and referred to their personal physician for additional evaluation prior to further consideration for participation in this study. Baseline food intake will be assessed from diet history including multiple replicate 24-hour recalls to estimate usual intake, customary eating pattern, and food frequency questionnaires. After confirmation of the participant meeting all inclusion and exclusion criteria, participants will be enrolled into the study intervention.

STUDY INTERVENTION

Intervention Description

This study's intervention includes 12 weeks (± 1 week) of supervised aerobic exercise training for the group randomized to Aerobic Exercise. The Control group will not be subject to an intervention as they will receive standard care only (see *Standard Care*). Subjects randomized to the Control group will be given the option of an off-label exercise intervention. Therefore, Control group participants will be allowed to enroll in the AE training group after completion of the original Control group trial period.

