Group Assignment Procedure

Following enrollment into the study, participants will be randomized into either the Aerobic Exercise group (n=30) or Control group (n=30. Females and males will be equally distributed between the groups. Regardless of group assignment, each participant will receive standard care for diabetes management.

Aerobic Exercise Training

Every AE training session will be supervised by the research team using established protocols [22-28]. Training sessions will take place at the Central Campus Recreation Building (CCRB), Domino Farms, or other University of Michigan recreation facility (e.g., North Campus Recreation Building) approximately 5 days per week and include treadmill walking, cycling, elliptical, or other related modes of exercise. Briefly, AE training will begin with a 2-week ramp-up, familiarization period of progressing exercise intensity and duration. Training intensity will progress from 55% VO₂max for week 1 (40 min session), to 60-65% VO₂max for week 2 (50 min session), to ~70% VO₂max for all other weeks (50 min session). Subjects will perform a brief warm-up and cool-down (~5 min each) that may include stretching or other light exercises for a total exercise time of 60 min. Subjects will wear heart rate monitors during each training session to provide real-time feedback of target heart rate. Intensity, duration, resting and exercise heart rates, and blood pressures will be recorded for each session. Exercise duration and intensity may be adjusted at the discretion of the PI, Co-I, or study team member. Followup VO₂max tests will be performed at approximately weeks 4 and 8 to monitor progress. AE intensity will be adjusted to match the prescribed training intensity [23, 24, 29-32]. Subjects in the AE training group will also conduct foot safety checks with the research team to monitor foot ulcers/blisters. Relevant findings during foot inspections will be addressed with the participant and study physician. Non-weight bearing exercise may be implemented if the subject is limited.

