Concomitant Medications

[figure not shown]
Subjects participating in this study will be diagnosed with T2DM and therefore have unique medical needs. In addition to the screening provided in this study, each participant will be encouraged follow their personal physician's guidance. Prior to and during the intervention period, all medication use, dose and frequency will be documented

Assessment of Subject Compliance with Study Intervention

Subject compliance will be regularly assessed and documented by the research team. Participants enrolled in the AE group will have contact with the research team approximately 5 days per week and the Control group will have contact with the research team approximately twice per month. Compliance will be determined through routine personal communication and primarily evaluated based on exercise training attendance (Aerobic Exercise group only), physical activity tracking, and dietary monitoring. Subjects in the Aerobic Exercise group are expected to complete \geq 80% of the training sessions over the course of the 12 weeks.

STUDY SCHEDULE AND PROCEDURES

Figure 3 provides a brief study summary of the study schedule. This study is composed of initial subject screening and enrollment based on established inclusion and exclusion criteria and randomization to 12 weeks of Aerobic Exercise training or Control Period (both including established Standard Care practices). Participants will all complete the same baseline testing and final study visit testing. Subjects randomized to the AE group will also undergo follow-up testing at weeks 4 and 8 (\pm 1 week) to adjust exercise training parameters. All testing will occur at the Michigan Clinical Research Unit (MCRU), Michigan Nutrition Obesity Research Center (NORC), Domino Farms, Frankel Cardiovascular Center (CVC), and/or Central Campus Recreation Building (or other University recreation building) and based on subject schedules, will include a total of approximately 7 visits.

Scheduling Flexibility

Due to limitations of the subject's schedule, study team, experimental approach, and/or clinic availability, some procedures may be excluded or adjusted from any given visit. Excluded or adjusted procedures will be at the discretion of the PI or Co-I and will not be considered a protocol deviation.

Subject Screening

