Initial screening of participants will occur via a website screening tool or telephone interview. During this time, the study will be described in detail and we will obtain information about age, body mass index (BMI), smoking and physical activity status, current medical conditions, health status and medications. Subjects who meet the initial screening criteria will be scheduled for a complete screening at the MCRU, CVC, Domino Farms, and/or CCRB. Verbal and written informed consent will be obtained during this

initial visit according to the guidelines of our Institutional Review Board. Subjects will be screened based on the inclusion and exclusion criteria. Screening procedures include a comprehensive medical history examination, blood draw, resting electrocardiogram, graded exercise stress test, and urine collection. In addition, pre-menopausal women will have a urine pregnancy test. All screening findings will be reviewed by the research team and study physician(s) (or CVC/Domino Farms physician) when appropriate.

Baseline Testing

Baseline testing procedures will be supervised by the research team and completed at the MCRU, CVC, Domino Farms, CCRB, and/or NORC. Testing includes measurement of basal metabolic rate, maximal aerobic capacity, cognitive assessment questionnaire (NIH ToolBox), body composition, OGTT, and insulin sensitivity. In addition, the Minnesota Leisure Time Physical Activity and Seven Day Physical Activity Recall Questionnaires will be administered to assess habitual physical activity levels. Subjects will also undergo an acute aerobic exercise bout (treadmill walking) coupled with microdialysis and muscle biopsies. Each of these testing procedures are critical for completion of the study objectives and evaluation of the study hypotheses.

Basal Metabolic Rate

Basal metabolic rate will be measured at Domino Farms, MCRU, CCRB, or CVC by the research team and/or medical staff. Subjects will initially rest quietly in their room for ~30 min. We will then measure their basal metabolic rate using a canopy-equipped metabolic cart for ~20 min.

Maximal Aerobic Capacity

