Body composition will be assessed by dual-emission X-ray absorptiometry (DEXA). DEXA scans determine components of body composition such as bone mineral density, lean body mass, fat mass, and segmental adiposity such as truncal fat and visceral fat mass. DEXA scans will be performed in the MCRU by the MCRU staff or a member of the study team.

Oral Glucose Tolerance Test (OGTT)

This standard test is utilized to detect and confirm the presence of diabetes. Briefly, a polyethylene catheter will be inserted into an antecubital or dorsal hand vein and the subject will drink a beverage containing 75 g of glucose. If a catheter is not successfully inserted, venipuncture for blood collection may be implemented. In addition, finger-sticks may also be utilized to assess blood glucose levels. A baseline blood draw will precede the consumption of the glucose drink along with blood draws approximately every 30 min for 3 h. Current use of physician confirmed diabetes medication, fasting glucose values \geq 126 mg/dL and 2 hr OGTT values \geq 200 mg/dL will be used as the criteria for type 2 diabetes [38]. Blood samples will be collected and immediately transferred to vacutainers, centrifuged, and stored at -80°C until analysis for blood glucose and insulin concentrations. OGTTs will take place at MCRU, CCRB, or Domino Farms and will be supervised by members of the study team after catheter insertion by the clinical staff or qualified research team member.

Measurement of Insulin Sensitivity

Whole body insulin sensitivity will be assessed using a 40 mU/m²/min hyperinsulinemic-euglycemic (glucose 90 mg/dL) clamp procedure as described

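### The protocol does not make randomisation wait for baseline testing, so baseline outcomes could be measured after the arm is known, and the OGTT's role in eligibility conflicts with its timing

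*Combined protocol and SAP*

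**What the plan says.** **Order of events.** Screening Procedures ends: "After confirmation of the participant meeting all inclusion and exclusion criteria, participants will be enrolled into the study intervention". Group Assignment Procedure continues: "Following enrollment into the study, participants will be randomized into either the Aerobic Exercise group (n=30) or Control group". Study Schedule and Procedures describes the study as "initial subject screening and enrollment based on established inclusion and exclusion criteria and randomization to 12 weeks of Aerobic Exercise training or Control Period", and the next sentence but one reads "Participants will all complete the same baseline testing and final study visit testing".

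**Content of each phase.** Subject Screening states: "Screening procedures include a comprehensive medical history examination, blood draw, resting electrocardiogram, graded exercise stress test, and urine collection". Baseline Testing lists basal metabolic rate, then "maximal aerobic capacity, cognitive assessment questionnaire (NIH ToolBox), body composition, OGTT, and insulin sensitivity", followed by activity questionnaires and the acute exercise bout with microdialysis and muscle biopsies.

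**The OGTT.** Its own section says: "This standard test is utilized to detect and confirm the presence of diabetes". The criteria for type 2 diabetes in that section begin "Current use of physician confirmed diabetes medication, fasting glucose values" and go on to the 2-hour OGTT value, joined by 'and'. Type 2 diabetes is an inclusion criterion.

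**The primary outcome.** Serum sRAGE is sampled before and after the 12 weeks of training. The draw is placed relative to training and not relative to randomisation.

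**The concern.** The arms are supervised exercise and standard care, so participants and training staff know the assignment once it is given. The available text describes neither concealment of the allocation nor blinding of the people who run the tests. In that setting the usual protection is to finish baseline before anyone knows the arm, and the protocol does not say that this is done.

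Two things are at stake.

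- **Behaviour before baseline.** Baseline is half of every pre-post contrast. Serum sRAGE is an ELISA and does not depend on effort, but the protocol's own background reports that acute exercise raises plasma cRAGE, including in people with type 2 diabetes. Someone who learns the arm and changes activity before the baseline draw could shift the primary baseline. The requirement of at least 24 hours since the last exercise before metabolic measures limits acute carry-over but not a longer change of habit.
- **Drop-out before baseline.** The baseline phase includes biopsies, microdialysis and an overnight stay with a clamp, and Reasons for Withdrawal names discomfort with sampling. If the arm is known by then, willingness to go through these tests could differ by arm. Those who leave would have an allocation but no baseline, and no analysis population is defined that says how they are handled.

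The OGTT raises a related problem: a test described as confirming an inclusion criterion appears in a phase that the text places after enrolment.

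**Working it through.** No figure in the plan bears on this point, so the check sets the sections side by side.

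**Step 1: the order of randomisation and baseline.**

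| Section | What it fixes |
|---|---|
| Screening Procedures | Criteria confirmed, then enrolment |
| Group Assignment Procedure | Enrolment, then randomisation |
| Study Schedule and Procedures | Screening, enrolment, randomisation; baseline testing named afterwards |
| Initial Exercise Bout | Takes place after baseline testing; counts as session 1 for those randomised to training |
| Figures 2 and 3 | Not available |

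The first three rows put randomisation next to enrolment, with nothing between them. The fourth fits either order: allocation could come before baseline testing, or between baseline testing and the bout. No available row makes randomisation wait. Scheduling Flexibility also allows procedures to be dropped or adjusted at the investigators' discretion without this counting as a deviation, so the text does not hold the sequence in place indirectly.

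**Step 2: which baseline measures are exposed.**

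- *Serum sRAGE.* Screening blood (20 ml in Table 1) is described only for clinical laboratory tests. The baseline visit accounts for 280 ml. The protocol does not say which draw supplies baseline sRAGE, but the baseline visit is the likelier source, so the primary baseline could follow allocation.
- *Muscle RAGE.* The first biopsies are tied to the baseline acute exercise bout. Exposed.
- *Insulin sensitivity.* The clamp is part of the baseline phase. Exposed.
- *VO2max.* Screening Procedures includes a graded stress test with VO2, and Maximal Aerobic Capacity says VO2max is taken from the graded test. That points to a measurement before allocation. However, Baseline Testing lists maximal aerobic capacity again, and the section on the acute exercise bout expects VO2max about a week beforehand. It is therefore unclear which test is the baseline. Less exposed.

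**Step 3: the OGTT and eligibility.**

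1. Type 2 diabetes is an inclusion criterion.
2. All criteria are confirmed before enrolment (Screening Procedures).
3. The OGTT is used to confirm diabetes (OGTT section).
4. The OGTT is absent from the test lists in Screening Procedures and Subject Screening. Before the intervention it appears under Baseline Testing and, in Metabolic Control Period, within about a week of the clamp stay.

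Statements 2, 3 and 4 cannot all hold for a participant whose diabetes is confirmed by the OGTT. They can hold for one confirmed by other evidence at screening. The protocol does not say which participants fall into which group.

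**The case against.** The strongest objection is that this reads the order of paragraphs as the order of events. No sentence says randomisation precedes baseline testing. The schedule sentence pairs baseline with final testing, so it may only be saying that both arms have the same tests. The initial exercise bout fits randomisation after baseline equally well, and the missing figures may settle the matter. All of this stands. A reader might infer that the protocol orders allocation before baseline, and the documents do not support that. They support only that the text, followed as written, permits it and that nothing available prevents it. A figure showing the order would help, but the rule for revealing the allocation should still be written out.

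A reader might also infer that a failed OGTT leads to exclusion after randomisation. No section says that a participant below the threshold is removed, and the written rule is eligibility first. Medication use and fasting glucose are listed beside the 2-hour value. History, A1C and a metabolic panel are obtained at screening, and the OGTT is repeated at the final visit, so it also serves as an outcome measure. Many participants could therefore be confirmed before enrolment. What remains is the mismatch between sections. It matters most for people not yet on medication, and the protocol does anticipate newly diagnosed participants.

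A third tempting reading is that effort on the baseline VO2max test will be biased by knowledge of the arm. The screening graded test answers most of that. VO2max is also a secondary outcome, and the primary outcome does not depend on effort.

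**Conclusion.** The concern holds in a limited form. The protocol does not fix when allocation is generated or revealed relative to baseline testing, and its text order allows allocation first. In an unmasked trial this leaves baseline sRAGE, muscle RAGE and the clamp open to differences in behaviour or drop-out by arm. The sections on the OGTT and on confirming eligibility contradict each other wherever the OGTT is the confirming evidence, and they must be reconciled.

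The size of any bias cannot be estimated. The documents give no shift in baseline attributable to knowing the arm, no rate of OGTT results below the threshold and no expected loss before baseline. A reader might want to attach an inflated false-positive rate, but any such rate would be t-test arithmetic on a shift chosen by the reader, with no source in the documents.

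The conclusion rests on two assumptions: that Figures 2 and 3 do not already place randomisation after baseline, and that baseline sRAGE comes from the baseline visit. If the team already randomises after baseline, the change simply records its practice.

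**What to change.** Amend Group Assignment Procedure along these lines:

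> The allocation is generated, and revealed to participants and staff, only after eligibility has been confirmed (including by any OGTT used for that purpose) and all baseline outcome measures, including blood for sRAGE, muscle biopsy and clamp, are complete.

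Then align three other sections:

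- **Screening Procedures:** reconcile its requirement that all criteria be confirmed before enrolment with the OGTT's confirming role, and say whether the OGTT contributes to eligibility, serves as a baseline measure, or both.
- **Study Schedule and Procedures:** state the sequence in words, with randomisation after baseline testing.
- **Baseline Testing:** say whether the screening graded test or a separate test is the baseline VO2max.

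The cost is small. No visit or procedure is added. The initial exercise bout already follows baseline testing in both arms, so allocation is needed only around that point. The downside is that training sessions are scheduled slightly later. People who leave during baseline would no longer be counted as randomised, so the text should also say whether the 75 to be enrolled and the 30 per arm are counted at enrolment, at randomisation or at completion.

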- **Time Commitment**: Some participants may find the time commitment associated with this study too burdensome for their schedule. The study coordinator will discuss this time commitment prior to enrollment.
- Schedule Conflicts: Some participants may find it difficult to determine times they are available to come in for study visits. The study coordinator will also discuss preferred visit start times prior to enrollment to limit potential schedule conflicts.
- **Discomfort:** Participants may experience discomfort during blood and tissue sampling procedures and wish to discontinue the study. Prior to enrollment, the study coordinator will discuss all procedures and answer any questions participants may have concerning sampling procedures.
- **Unforeseen Reasons:** There may be other reasons participants may withdrawal from the research study that are unknown at this time.

Handling of Withdrawals

The participants right to withdraw from the study will be respected and will occur within the timeframe they request. In the event of a participant withdrawal, samples and data collected during their participation will be stored for future use or destroyed, based on the participants request.

Termination of Study

The research staff reserves the right to suspend/terminate subject's participation in this study at any time. This decision will be communicated to the participant and a reasonable effort will be made to mitigate/avoid this outcome. Potential study suspension/termination reasons include:

- **Ineligibility**: The subject's eligibility changes during the study
- Safety: The research has become harmful to the participant
- **Health**: The subject's health condition changes and requires treatment which affects the study outcomes
- **Incompliance**: Subject fails to follow the study guidelines
- Cancelation: The research study is canceled or suspended

Accountability Procedures for the Study Intervention

The research team will communicate internally weekly to discuss study progress and ensure all objectives and guidelines are met. From a participant perspective, agreement to enroll in the study will necessitate adherence to all study guidelines. The research staff will have regular contact (approximately 5 days/week) with subjects in the Aerobic Exercise group and will meet approximately twice monthly with the control group to monitor habits and study progress. We have found these interactions are indispensable for study adherence.

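### Staff may end study participation, not just training, and the plan asks no one so removed for the 12-week sRAGE sample, so the primary outcome can be lost unequally by arm

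*Combined protocol and SAP*

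**What the plan says.** The combined protocol and SAP gives staff a broad power under 'Termination of Study': "The research staff reserves the right to suspend/terminate subject's participation in this study at any time". What ends is participation in the study, not only in training. The reasons are presented as potential ones. They include non-compliance ("Subject fails to follow the study guidelines"), ineligibility ("The subject's eligibility changes during the study") and health ("The subject's health condition changes and requires treatment which affects the study outcomes"). The clause is softened by a promise that "a reasonable effort will be made to mitigate/avoid this outcome".

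'Accountability Procedures for the Study Intervention' adds that "agreement to enroll in the study will necessitate adherence to all study guidelines". It also describes unequal contact: "The research staff will have regular contact (approximately 5 days/week) with subjects in the Aerobic Exercise group and will meet approximately twice monthly" with controls. 'Assessment of Subject Compliance with Study Intervention' counts training attendance in the exercise group only, with at least 80% of sessions expected. Activity tracking and dietary monitoring are also compliance measures and are not limited to one arm.

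On what follows an exit, 'Handling of Withdrawals' deals only with participants who withdraw themselves, and only with material already in hand: "samples and data collected during their participation will be stored for future use or destroyed, based on the participants request". 'Study Schedule and Procedures' says in general terms that everyone has the same final testing, without mentioning people whose participation has been ended. The primary outcome is the change in basal serum sRAGE from before to after 12 weeks.

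**The concern.** A person whose participation is ended before week 12, and who is not asked for the final sample, has no primary outcome. The listed reasons describe events that can follow randomisation and that the assigned arm can influence. Exercisers have one more way to be found non-compliant (missed sessions) and many more occasions on which it would be seen: about five contacts a week against about two a month.

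If those removed would have had a different sRAGE change from those kept, and removal differs by arm, the 12-week comparison no longer estimates the effect of assignment to exercise versus standard care. Removing poor attenders would tend to favour exercise if they respond less. The sign reverses if those removed had the larger changes.

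'Statistics and Sample Size Considerations' names no analysis population and no sensitivity analysis for missing data. Adherence is not among the covariates it names.

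**Working it through.** **What the plan's own figures give.** 'Statistics and Sample Size Considerations' enrols 75 and expects 20-25% attrition, leaving 60. At 20%, 60/(1 - 0.20) = 75, as stated. At 25%, 75 × 0.75 = 56. Planned losses are therefore 15 to 19 people, not split by arm or cause. 'Study Design' and 'Group Assignment Procedure' speak of 60 randomised, 30 per arm. Both sizes are used below.

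**Assumed inputs (none is in the documents).** A share f = 0.20 or 0.25 are non-adherers. Their sRAGE change is lower by d = 0.5 or 1.0 SD of the change. Shares rE and rC of the non-adherers are terminated in the exercise and control arms. The true effect of training is zero.

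**Formula.** After termination the share of non-adherers left in an arm is f(1 - r)/(1 - f·r), so

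bias = d × [ f(1 - rC)/(1 - f·rC) - f(1 - rE)/(1 - f·rE) ].

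For f = 0.20, d = 1, rE = 0.5, rC = 0: 0.20 - 0.10/0.90 = 0.20 - 0.111 = 0.089 SD. For f = 0.25, d = 1: 0.25 - 0.125/0.875 = 0.25 - 0.143 = 0.107 SD.

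**Results.** Rejection rates come from a t test on change, used as a simple stand-in for the group-by-time test, with at least 40,000 simulated trials per cell. The order is (f, d) = (0.20, 0.5), (0.20, 1), (0.25, 0.5), (0.25, 1).

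| Terminated | Bias (SD) | Rejection, 30 v 30 | Rejection, 37 v 38 |
|---|---|---|---|
| Half of non-adherers, exercise only | 0.044, 0.089, 0.054, 0.107 | 5.2, 5.9, 5.4, 6.3% | 5.5, 6.6, 5.5, 6.8% |
| Half in exercise, a quarter in control | 0.023, 0.047, 0.029, 0.057 | 5.0-5.7% over both sizes | |
| Half in both arms | 0 | about 5% | about 5% |

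The first row removes 10-12.5% of the exercise arm, leaving about 26-27 against 30. Repeat simulations put the top of that row at up to 6.7% (30 v 30) and 7.0% (37 v 38), so these rates are best read as roughly 5-7%.

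If only 5% of exercisers are terminated (q = 0.05), all of them non-adherers, the bias is d·q(1 - f)/(1 - q). This runs from 0.5 × 0.05 × 0.75/0.95 = 0.020 to 1.0 × 0.05 × 0.80/0.95 = 0.042 SD, with rejection at 5.0-5.3%.

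**If only exercisers can be non-adherent.** The same termination overstates the as-randomised effect by a simulated 0.043, 0.090, 0.054 and 0.106 SD. The bias therefore does not need non-adherers among controls. The rejection rates in the table do.

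**Does the mixed model repair it?** For the first row, a random-intercept model with baseline and week 12 only has the same expected bias (0.044, 0.089, 0.054, 0.107). 'Follow-up Testing' has blood drawn from everyone at weeks 4 and 8, but no section says it is assayed for sRAGE. If it were (assuming linear drift in non-adherers and between-visit correlation 0.5-0.8), the bias would be 0.031-0.080 SD for termination after week 8 and 0.038-0.095 SD for termination after week 4. About 70-90% of it would remain.

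**A different loss model.** Suppose instead that the least adherent 10-25% of the exercise arm are all lost, with a correlation of 0.2-0.5 between adherence and change. The bias is r·φ(z_q)/(1 - q), here with q the share lost and r the correlation. This gives 0.04-0.21 SD, and type I error of 5.3-13% at 30 per arm. It is a heavier loss than the main illustration and shows only how far the answer depends on the assumptions.

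**The case against.** The strongest reply is that the effect is small and the trigger is not written down. Even with one-sided use, the bias is a fraction of a standard error: 0.044/√(1/27 + 1/30) = 0.17 at the low end and 0.107/√(1/26.25 + 1/30) = 0.40 at the high end. Attendance below 80% is not said to lead to termination. The reasons are only potential, staff must try to avoid using them, and remote training is allowed. Controls wear an activity device and meet the team too, so they can also be found non-compliant and losses may offset. The inflated rejection rates require non-adherence to predict sRAGE change even without a training effect, and equally in both arms. The covariate list is open-ended and includes weight, which may partly follow training. Voluntary withdrawal may well be the larger source of loss.

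All of that bears on size and likelihood, and it stands. It is why the point is conditional and the figures are illustrations. It does not supply the missing sample. Discretion leaves the loss in staff hands after allocation. The general statement that everyone completes final testing does not plainly reach a person whose participation has ended. The documents do not say that week 4 or week 8 sRAGE will exist to draw on.

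**Conclusion.** The concern holds as a conditional one. As written, the clause allows the primary outcome to be lost on post-randomisation grounds that bear more heavily on the exercise arm, and no section asks for the 12-week value afterwards. Whether it would be used, and which way it would push, cannot be derived from the documents.

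Under the stated assumptions the bias is modest: 0.04-0.11 SD if 10-12.5% of exercisers are terminated and no controls, 0.02-0.04 SD if 5% are, and zero if removal is equal. The rejection rates of roughly 5-7% apply only if non-adherence predicts sRAGE change in both arms. If it exists in the exercise arm alone, the 0.04-0.11 SD is overstatement of the as-randomised effect. The plan does not remove low attenders from the analysis as such. The defect is the uncollected 12-week sample. It merits correction because it is cheap to prevent and a sample never requested cannot be recovered at analysis.

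**What to change.** In 'Termination of Study', separate stopping training from leaving the study. For example:

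> Participants who stop or miss training, change medication or no longer meet entry criteria remain in follow-up unless they withdraw consent or are withdrawn for safety. They are asked to give the planned 12-week basal serum sample and are analysed in their assigned group.

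If the investigators prefer to leave the list of reasons untouched, a narrower sentence closes most of the gap: anyone whose participation is ended, who still consents and for whom it is safe, is asked for the 12-week serum sample. Either way, report terminations by arm and reason, and add a sensitivity analysis for values not missing at random. Attendance of at least 80% can define a supplementary analysis. The grounds for stopping training remain with the investigators.

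The cost is a few sentences and one already planned blood draw for people who would otherwise be lost. The estimate will include non-adherers and may be diluted. Loss through voluntary withdrawal of consent is not addressed by this change.
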